Project Design: Our project design involves the development of Perinatal DBT. We will follow patient-engagement strategies as delineated by the Centre for Healthcare Innovation. Specifically, we will adopt the *Valuing All Voices Framework* to guide our work with the vulnerable population we serve.¹⁴ This framework encompasses five key concepts with definitions that will guide our work: 1) Education and Communication, 2) Understanding and Acceptance, 3) Trust, 4) Relationship Building, and 5) Self-Awareness. In 2021, our interprofessional clinical team created a framework to guide our clinical care approach. Our framework is based on an integrated psychosocial perinatal care model that we practice and delineates three domains: Social, psychological, and perinatal. Each domain intersects and describes aspects of interprofessional engagement to consider when tailoring care for each person with complex needs. Birth experience is at the centre of these domains. Examples of our IPPC model that we offer are reflected in the intersecting domains and are as follows but not limited to social supports, housing, food safety, meaningful employment, neurodiversity health, gender identity, trauma informed care and support, addictions treatment, coping skills, cultural supports, self-care, parenting tools, grief counselling, perinatal psychiatric care, emancipation from domestic violence, and others (Appendix A). Finally, in adopting and considering the *Valuing all Voices Framework*, we will evolve our approach to patient-informed care, and it will support and guide us to use a health equity and a social justice lens to guide our patient-engaged approach.

The purpose of this study is to understand if an adaptation of the standard DBT is culturally safe. We have engaged and invited an Indigenous Elder to co-lead and inform the adaptation of DBT.

Specific Aim 1: To evaluate patient feedback from evidence informed adapted DBT in the context of complex care patients.

Specific Aim 2: To understand patient perspectives of the DBT skills sessions with the participation of an Elder.

Experimental Methods of Engagement

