Data Collection: Pre and post session Interviews and Appreciative Inquiry (see data analysis stage) will be the two methods of engagement. The purpose of the qualitative pre and post session interviews is to glean an understanding of what the patients understanding of the benefit of DBT and their needs and then to

understand how DBT impacted health and well-being at the end of the DBT skills session. Our team will use a semi-structured interview guide for the pre-interviews and develop the post interview guide towards the end of the nine months. The post interview guide will be informed by what we learn and feedback from the Elder throughout this process and from the pre-interview data. Our IPPC team supports 35 to 40 patients during any given month, with deliveries balanced by new intakes. Our end goal is to have 8 to 10 patients participate in DBT skills sessions, with a maximum of 15 per cycle.

During our pre and post interviews we will gather qualitative data to articulate patient care priorities and to understand the impact of the DBT skills sessions. We anticipate each interview to be approximately one hour in a neutral space provided at HSC. Because these patients are under our care, we will provide continual support throughout the process in terms of mental health supports and other supports.

We will also use Appreciative Inquiry to guide our reflection in our team outside of our patient engagement processes. Therefore, another point of data collection for this project will entail an IPPC team meeting at 6 months and 12 months to reflect on our understanding, interpretation, and analysis from our engagement with patients. We will have an Appreciative Inquiry facilitator lead our team meetings to ensure reflexive practice amongst our IPPC team throughout the time of this project.

Data Analysis

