As we engage patients to gain an understanding of patient experience and impact of DBT skills sessions, we will use a *collaborative* Appreciative Inquiry approach in these dialogues (i.e., interviews). Appreciative inquiry (AI)¹⁶ is a strengths-based approach that identifies optimal care experiences to define care strategies that are successful from a patient perspective; it begins with “what works” rather than staying mired in “what doesn’t.” Additionally, AI identifies patient strengths to provide a conceptual scaffold upon which to build a care model grounded in lived experience and will use this approach to analyze the client interviews. This method of engagement will guide our interprofessional clinical team to ensure we employ reflexive practice, explore patient expectations, and respect and hear the patient’s voice in research design and development to improve their care experiences. This design partnership supports positive change among the clinical team members and facilitate true interprofessional work, and ultimately ensure the patient is at the centre of our care delivery and team.

In analyzing the data from the pre and post interviews, we will complete a content analysis from the recorded interviews. We will all code the data and come together to cross-check and validate our interpretations of this experience via the Appreciative Inquiry process at one of our clinical team meetings without patients involved. This will ensure we have an opportunity as a clinical team to reflect on process. Our patients will have the opportunity to review the transcribed interviews and the analysis by the team to ensure accuracy of their perspectives.

All our analyses from this project will be an iterative process as we go back and forth to both the IPPC the Valuing All Voices Frameworks (Appendix A) to analyze and validate our findings in relation to the constructs reflected in each. We will adapt DBT based on the feedback and insight from the patients.

Safety and Risk

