We anticipate low potential risks and discomforts in this project. Patients will be asked about their experiences surrounding DBT skills sessions offered by the Interprofessional Psychosocial Perinatal Care team which could bring up past trauma and discomfort. The care team will support patients who participate in DBT skills sessions and will offer the services of the clinic's perinatal psychiatrist if the patient chooses. An Indigenous Elder will be available to speak with patient if they choose. Because these patients are under our care, we will provide continual support throughout the process in terms of mental health supports and other supports. The PI or [name] will follow up with the affected patient at an appropriate time.

[name], [name], and [name] will meet every month to discuss the progress and safety of the project. All adverse events and unanticipated problems will be resolved immediately after the event and Shared Health Impact will be notified.

Privacy

The Patient names and other identifying information will only be captured on the Patient Recruitment postcard and the Pledge of Confidentiality. These documents will be uploaded to a secure server at the University of Manitoba (UM) by the research coordinator (RC) and only the PI and RC will have access to the folder. The hard copies of the documents will be stored in a locked filing cabinet in the PI's locked office at the University of employment, which only the PI has access to that filing cabinet. The audio-recording will not contain identifying information but rather the patient's assigned code.

[name] work computer is password protected and the passwords are only known by the individual's whose computer it belongs to. Any confidential information that needs to be printed and stored will be placed in a locked cabinet in the RC's office, which is accessed through a locked door.

The audio-recordings and digital files will be deleted from the UM server and DataVerse. All physical data will be confidentially shredded and discarded.

The data will be stored for 7 years.

Outcomes and Knowledge Translation

Anticipated outcomes: We anticipate we will garner new knowledge from the patient pre/post interviews. And from this we can adapt DBT to ensure it is culturally safe. We are planning research priorities and future grant development and will include this process.

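### The stated interview purposes and the Appreciative Inquiry lens do not match the question of whether the adapted DBT is culturally safe

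*Protocol*

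**What the plan says.** **The question.** Protocol, Project Design: "The purpose of this study is to understand if an adaptation of the standard DBT is culturally safe". Hypothesis and Outcomes lists culturally safe adaptation as one of two outcomes. Specific Aim 2, the aim closest to this, is worded openly: "To understand patient perspectives of the DBT skills sessions with the participation of an Elder".

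**What informs the answer.** Under Outcomes and Knowledge Translation the team expects to "garner new knowledge from the patient pre/post interviews. And from this we can adapt DBT to ensure it is culturally safe". The interviews are not the only route. The background text, Project Design and Experimental Methods of Engagement also give the Elder a co-leading role in the sessions, with feedback that shapes the adaptation.

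**What the interviews are for.** Under Data Collection, the pre interviews explore how patients see the benefit of DBT and what they need. The post interviews are to "understand how DBT impacted health and well-being at the end of the DBT skills session". Both are to "gather qualitative data to articulate patient care priorities and to understand the impact of the DBT skills sessions". The pre interviews use a semi-structured guide. For the post interviews the team will "develop the post interview guide towards the end of the nine months", drawing on Elder feedback and the pre-interview data.

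**How the interviews are conducted and analysed.** Data Analysis names Appreciative Inquiry for the dialogues with patients, for the analysis of those interviews, and for the cross-check at a clinical team meeting held without patients. It describes the method as strengths-based, starting from what goes well, and as one that "identifies optimal care experiences to define care strategies that are successful from a patient perspective". A content analysis of the recordings is also named.

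**The concern.** A study that asks whether an intervention is culturally safe needs a method that can return the answer no. Here the declared interview topics do not include cultural safety, and the declared lens at all three stages (asking, analysing, cross-checking) looks first for success. That lens suits the building of a care model. On its own it is a weak instrument for finding out that a session felt unsafe or disrespectful.

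At stake is how an absence of negative findings would be read. If few unsafe experiences are reported, the team could not readily tell whether the sessions were safe or whether the matter was not raised. It would also have less information on what to change when it adapts DBT from patient feedback. The protocol's own Anticipated Barriers section expects power inequities and low trust in health care, which makes it less prudent to rely on patients to volunteer criticism unprompted.

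**Working it through.** The study is qualitative and the plan gives no figure on this point, so there is nothing to recompute. The check sets the stated purpose beside each stated step.

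1. **Purpose.** Project Design asks whether the adapted DBT is culturally safe. This is an evaluative question with two possible answers.
2. **Link to the interviews.** Outcomes and Knowledge Translation relies on pre/post interview findings for culturally safe adaptation, alongside the Elder's contribution. The interviews therefore carry part of the question.
3. **Topics.** The purposes in Data Collection are benefit, needs, impact on health and well-being, care priorities, and impact of the sessions. Cultural safety is not named. A patient could raise it under impact, but nothing calls for it.
4. **Lens.** Data Analysis applies Appreciative Inquiry to the interviews, the analysis and the cross-check.
5. **Steps that could bring negative accounts to light.**
   - *Content analysis* is open to any theme, but no category or search for negative cases is stated.
   - *Patient review* of transcripts and analysis is optional and aimed at accuracy. It comes after the interview, so it is not designed to elicit what was never asked.
   - *Elder input* to the post guide could introduce the topic, but the protocol does not require it to.
   - *Framework comparison.* The five Valuing All Voices concepts listed in Project Design include trust, and the care-model examples include cultural supports and trauma-informed care. These are related constructs, but none is a stated search for unsafe experiences.
   - *Open wording* in Specific Aims 1 and 2, and in Safety and Risk where patients are asked about their experiences of the sessions, permits negative accounts without asking for them.
   - *External readiness* speaks of patients debriefing on maternity care whether good or bad, and says the study will give room for such sharing. This shows intent, but it is not an interview topic or an analysis step.

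**Result.** Each item in step 5 permits a culturally unsafe experience to be heard. None requires it to be asked about or looked for in coding.

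**The case against.** The strongest reply is that this is silence rather than contradiction. Questions and codes normally sit in guides and codebooks. The pre-interview guide is not shown, the post guide is deliberately left to be written with the Elder, the standard operating procedures are listed but not shown, and the framework figures in Appendix A are missing from the text. The design is meant to be reciprocal and flexible. The Elder, who co-leads the sessions, can bring safety problems to the team without any interview question. External readiness welcomes bad experiences as well as good. A predefined disconfirming-case code is also only one convention of qualitative rigour.

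Much of this stands. The unseen guides and figures may already cover the topic, so no claim can be made about their content. The Elder is a genuine second route.

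A reader might infer that Appreciative Inquiry shuts out negative accounts, so that the study cannot detect unsafe sessions. The document does not support this: the method is described as starting from what works, not as stopping there, and several open channels remain. Nor are the interviews the sole source for the adaptation.

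What does not fall away is that the protocol itself states the interview purposes and the analytic lens. Those stated choices, followed as written, are poorly suited to its stated question. That goes beyond detail left to another document.

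**Conclusion.** The point holds at protocol level. The stated interview purposes leave out cultural safety, and the stated lens starts from success, while the study's purpose is to learn whether the adapted DBT is culturally safe. Culturally unsafe experiences may be under-detected. The size of any under-detection cannot be computed, because the document gives nothing from which to derive it.

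The conclusion assumes that the interviews and analysis follow the purposes and lens as written. If the unseen guides already ask about unsafe experiences, the remaining task is to bring the protocol text into line with them. This is a worthwhile low-cost improvement. It is not an error in a stated figure, and it is not a reason to abandon Appreciative Inquiry.

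**What to change.** Keep Appreciative Inquiry and make two additions.

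- **Data Collection.** Add cultural safety to the post-interview purposes, with a few neutral and negative open questions: for example, whether anything felt unsafe, disrespectful or unhelpful, and what the patient would remove or change. Word them with the Elder, whose input to the post guide is already planned, and set them before the first post interview takes place.
- **Data Analysis.** Add a disconfirming-case category to the content analysis, review those cases at the planned team cross-check, and report them descriptively, including when there are none.

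**Cost.** A few questions in a guide still to be written and one coding category. Interviews become slightly longer and the conversation less purely strengths-based. Direct questions about unsafe experiences may also add to participants' discomfort. Safety and Risk already anticipates discomfort of this kind and plans support from the care team, the perinatal psychiatrist and the Elder.

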Appendix A: Frameworks

[figure not shown]

Figure 1. Interprofessional Psychosocial Perinatal Care (IPPC) Framework.²⁰

Figure 2.

Revised *Valuing All Voices Framework* image with input from study participants.¹⁴
